### Other Exclusions

- [30] In the opinion of the investigator, have other issues that would interfere with compliance with the study requirements and completion of evaluations required for this study.
- [31] Are investigator site personnel directly affiliated with this study and/or their immediate families. Immediate family is defined as a spouse, parent, child, or sibling, whether biological or legally adopted.
- [32] Are Lilly employees or its designee or are employees of third-party organizations (TPOs) involved in the study.
- [33] Are unwilling or unable to comply with the use of a data collection device.

### 6.3. Lifestyle Restrictions

No changes in lifestyle or dietary requirements are required during the study.

### 6.4. Screen Failures

Individuals who do not meet the criteria for participation in this study (screen failure) may be considered for rescreen once, with approval from Lilly for only the criteria shown below. The interval between screening and rescreening must be at least 45 days or longer if required for the specified timeframes in the inclusion/exclusion criteria or concomitant medications requirements. If rescreening is performed, the individual must sign a new ICF and will be assigned a new identification number.

- Inclusion Criterion 1. If patients are less than age 18 at time of informed consent, they may be rescreened if they reach age 18 during the study enrollment period.
- Inclusion Criterion 8
- Exclusion Criterion 11
- Exclusion Criterion 13
- Exclusion Criterion 15
- Exclusion Criterion 27

Patients using a concomitant medication that requires a stable dose for a specific duration prior to Visit 2 may be rescreened if additional time is needed to meet the duration requirement.

In addition, after consultation with and approval by a Lilly Medical representative, a patient may be rescreened if there is an unexpected technical difficulty with the electronic diary capture during the prospective baseline period.

## 7. Treatment

### 7.1. Treatments Administered

This study involves a comparison of galcanezumab 120 mg (with an initial 240-mg loading dose) administered by subcutaneous injection once monthly with placebo. Sites will administer injections of investigational product (galcanezumab or placebo) at 3 office visits during the double-blind treatment phase and galcanezumab at 3 office visits during the open-label treatment phase (Section 2).

Possible injection sites include the abdomen, thigh, and upper arm. The buttocks may also be used, if needed.

The investigator or his/her designee is responsible for the following:

- maintaining accurate records of investigational product dispensing
- at the end of the study, returning all unused medication to Lilly, or its designee, unless the sponsor and sites have agreed all unused medication is to be destroyed by the site, as allowed by local law

#### 7.1.1. Packaging and Labelling

Galcanezumab and matching placebo (excipients only) will be supplied as an injectable solution in 1-mL, single-dose, prefilled, disposable manual syringes with study-specific labels. Each syringe of galcanezumab is designed to deliver galcanezumab 120 mg. The syringes (and contents) containing either galcanezumab or placebo will be visibly indistinguishable from each other. Syringes will be supplied in cartons, with the appropriate quantity of syringes specific to the planned dispensing schedule of investigational product.

Clinical trial materials will be labeled according to the country's regulatory requirements.

#### 7.1.2. Medical Devices

The manufactured medical devices provided for use in the study are prefilled syringes.

### 7.2. Method of Treatment Assignment

Patients who meet all criteria for enrollment will be randomized to double-blind treatment at Visit 3. Assignment to treatment groups will be determined by a computer-generated random sequence using an interactive web-response system (IWRS). The IWRS will be used to assign double-blind investigational product to each patient. Site personnel will confirm that they have located the correctly assigned package by entering the confirmation number found on the package into the IWRS.

To achieve between-group comparability, the randomization will be stratified by country and baseline migraine frequency (<8 MHDs versus  $\geq 8$  MHDs). To ensure an appropriate balance of patients with low- and high-frequency MHDs, the sponsor will stop enrollment of low-frequency patients if the number exceeds an estimated 292.

### **7.2.1. Selection and Timing of Doses**

This is a fixed-dose study. The actual time of all dose administrations will be recorded in the patient's electronic case report form (eCRF).

### **7.3. Blinding**

This is a double-blind study. Blinded transition to open-label treatment phase and/or post-treatment follow-up phase is included in this study.

To preserve the blinding of the study, a minimum number of Lilly personnel will see the randomization table and treatment assignments before the study is complete. After the reporting database is locked for statistical analysis of the double-blind treatment phase, a limited number of Lilly personnel will be unblinded to complete the study report and prepare for submission. However, study sites, patients and all Lilly personnel directly involved in the ongoing open-label and post-treatment follow-up phases will remain blinded to patients' double-blind treatment assignment.

Emergency unblinding for AEs may be performed through the IWRS. This option may be used ONLY if the patient's well-being requires knowledge of the patient's treatment assignment. All unblinding events are recorded and reported by the IWRS.

If an investigator, site personnel performing assessments, or patient is unblinded, the patient must be discontinued from the study. In cases where there are ethical reasons to have the patient remain in the study, the investigator must obtain specific approval from a Lilly Medical representative for the patient to continue in the study.

In case of an emergency, the investigator has the sole responsibility for determining if unblinding of a patient's treatment assignment is warranted. Patient safety must always be the first consideration in making such a determination. If an emergency unblinding occurs, Lilly must be notified as soon as possible.

### **7.4. Dose Modification**

Dose modifications are not permitted in this study.

#### **7.4.1. Special Treatment Considerations**

During the post-treatment follow-up period, patients will not receive galcanezumab or placebo. After completion of Visit 10 (Month 6) assessments, if clinically warranted due to a worsening of symptoms, patients may start migraine prevention medications at the discretion of the investigator. The list of allowed preventive medications is provided separately.

### **7.5. Preparation/Handling/Storage/Accountability**

The packaged investigational product must be stored according to the storage requirements printed onto the packaging label.

To administer the galcanezumab injections, sites are to refer to the pharmacy binder for the preparation and handling instructions of the packaged pre-filled syringes.

## 7.6. Treatment Compliance

Investigators will be required to document the administration of investigational product in the eCRF.

Investigational product must be administered as indicated in the Schedule of Activities (Section 2). If the investigator is unable to administer the investigational product in the allowed window, then the situation should be discussed with Lilly to determine if the patient may continue.

## 7.7. Concomitant Therapy

Acute treatment of migraine or headache is allowed throughout the study but with some limitations. Patient will be asked to capture usage of any acute migraine or headache medication or not via ePRO device during Study Periods II, III, IV, and V. Acute migraine or headache medication name, dose, and date will be recorded by patients during Study Periods II, III, IV, and V on a headache medication log, which will be returned to site staff at each office visit in the study.

Treatments used for the prevention of migraine, including migraine preventive treatments as defined in Exclusion Criterion [16], or any other medications as well as non-pharmacological interventions aiming to prevent migraine, are not allowed at any time during Study Periods II through IV. Patients should have discontinued all migraine preventive treatments at least 28 days prior to Visit 2. Botulinum toxin A or B in the head or neck area for therapeutic use should be discontinued within 4 months prior to Visit 2.

The list of medications allowed or not allowed will be provided separately in the operation manual. Any changes in the list will be communicated to investigators and will not constitute a protocol amendment.

## 7.8. Treatment after the End of the Study

### 7.8.1. Study Extensions

Not applicable.

### 7.8.2. Continued Access

Investigational product will not be made available to patients after conclusion of the study.

## 8. Discontinuation Criteria

Patients who discontinue the investigational product during the double-blind treatment phase (Study Period III) or open-label treatment phase (Study Period IV) will proceed immediately to Study Period V.

### 8.1. Discontinuation from Study Treatment

#### 8.1.1. *Permanent Discontinuation from Study Treatment*

Discontinuation of the investigational product is required in cases of pregnancy.

Possible reasons leading to permanent discontinuation of investigational product are as follows:

- **Subject Decision**
  - the patient requests to discontinue investigational product.
- **Discontinuation due to a hepatic event or liver test abnormality.** Patients who are discontinued from investigational product due to a hepatic event or liver test abnormality should have additional hepatic safety data collected via eCRF.

Discontinuation of the investigational product for abnormal liver tests **should be** considered by the investigator when a patient meets one of the following conditions after consultation with the Lilly-designated medical monitor:

- ALT or aspartate aminotransferase (AST) >8-fold ULN
- ALT or AST >5-fold ULN for more than 2 weeks
- ALT or AST >3-fold ULN and TBL >2-fold ULN or international normalized ratio (INR) >1.5
- ALT or AST >3-fold ULN with the appearance of fatigue, nausea, vomiting, right upper-quadrant pain or tenderness, fever, rash, and/or eosinophilia (>5%)
- ALP >3-fold ULN
- ALP >2.5-fold ULN and TBL >2-fold ULN
- ALP >2.5-fold ULN with the appearance of fatigue, nausea, vomiting, right quadrant pain or tenderness, fever, rash, and/or eosinophilia (>5%)

Patients discontinuing from the investigational product prematurely for any reason should complete AE and other follow-up procedures per Section 2 (Schedule of Activities), Section 9.2 (Adverse Events), and Section 9.4 (Safety) of this protocol.

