## 2. Schedule of Activities

**Table CGAX.1. Schedule of Activities  
Protocol I5Q-MC-CGAX (Double-Blind Treatment Phase)**

Study Period (SP)	SP I- Screening	SP II- Prospective Baseline	SP III Double-Blind Treatment				
			30-45	14	16	30	30
(Target) Interval (days) since previous visit							
Allowable range (days) between visits	3-45	30-40 a					
Interval allowance (days)				+/- 5	+/- 2	+/- 2	+/- 2
Visit	1	2	3	4 b	5 l	6	7
Month			0	0.5	1	2	3
Assessments and Procedures							
Informed consent	X						
Inclusion/exclusion	X	X	X				
Demographics	X						
Physical examination	X						
Neurological examination c	X						X
Height	X						
Weight	X						X
Medical history	X						
Prespecified migraine history d			X				
ECG e	X		X				X
Vital signs f	X		X		X	X	X
Adverse events	X	X	X	X	X	X	X
Concomitant medications	X	X	X	X	X	X	X
ePRO and headache medication log training		X					
ePRO diary daily patient entries		X	X	X	X	X	X
Headache medication log		X	X	X	X	X	X

Schedule of Activities

Protocol I5Q-MC-CGAX (Double-Blind Treatment Phase)

Study Period (SP)	SP I- Screening	SP II- Prospective Baseline	SP III Double-Blind Treatment				
			30-45	14	16	30	30
(Target) Interval (days) since previous visit							
Allowable range (days) between visits	3-45	30-40 a					
Interval allowance (days)				+/- 5	+/- 2	+/- 2	+/- 2
Visit	1	2	3	4 b	5 l	6	7
Month			0	0.5	1	2	3
Clinical Laboratory Tests and Sampling Schedules							
Hematology	X		X				X
Clinical chemistry	X		X				X
HbA1c			X				X
Urinalysis	X		X				X
Serum Pregnancy (for women of childbearing potential) or FSH at Visit 1 (all other female patients) g	X						
Urine pregnancy g			X		X	X	X
Immunogenicity h			X		X		X
PK blood sample h					X		X
Study drug administered i			X		X	X	X j
Scales, Questionnaires, and Outcome Measures							
MIDAS			X				X
MSQ v2.1			X		X	X	X
MIBS-4			X		X	X	X
PGI-S			X				X
GAD-7			X				X
PHQ-9			X				X

Schedule of Activities, Protocol I5Q-MC-CGAX (Open-Label and Post-Treatment Phases)

Study Period (SP)	SP IV Open-Label			SP V Post-treatment		ET K
	(Target) Interval (days) since previous visit	30	30	30	60	
Interval allowance (days)	+/- 2	+/- 2	+/- 2	+/- 5	+/- 5	
Visit	8	9	10	11 b	12	
Month	4	5	6	8	10	
Assessments and Procedures						
Weight			X		X	X

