Neurological examination c			X		X	X
ECG e			X		X	X
Vital signs f	X	X	X		X	X
Adverse events	X	X	X	X	X	X
Concomitant medications	X	X	X	X	X	X
ePRO diary daily patient entries	X	X	X	X	X	X
Headache medication log	X	X	X	X	X	X
Clinical Laboratory Tests and Sampling Schedule						
Hematology			X		X	X
Clinical chemistry			X		X	X
HbA1c			X		X	X
Urinalysis			X		X	X
Serum Pregnancy (for women of childbearing potential) g			X		X	X
Urine pregnancy g	X	X				
Immunogenicity h			X		X	X
PK blood sample h			X		X	X
Study drug administered i	X	X				
Scales, Questionnaires, and Outcome Measures						
MIDAS			X		X	X
MSQv2.1	X	X	X		X	X
MIBS-4	X	X	X		X	X
PGI-S			X		X	X
GAD-7			X		X	X
PHQ-9			X		X	X

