### 9.2. Adverse Events

Investigators are responsible for monitoring the safety of patients who have entered this study and for alerting Lilly or its designee to any event that seems unusual, even if this event may be considered an unanticipated benefit to the patient.

The investigator is responsible for the appropriate medical care of patients during the study.

Investigators must document their review of each laboratory safety report.

The investigator remains responsible for following, through an appropriate health care option, AEs that are serious or otherwise medically important, considered related to the investigational product or the study, or that caused the patient to discontinue the investigational product before completing the study. The patient should be followed until the event resolves, stabilizes with appropriate diagnostic evaluation, or is reasonably explained. The frequency of follow-up evaluations of the AE is left to the discretion of the investigator.

Lack of drug effect is not an AE in clinical studies because the purpose of the clinical study is to establish treatment effect.

After the ICF is signed, study site personnel will record via eCRF the occurrence and nature of each patient's preexisting condition(s), including clinically significant signs and symptoms of the disease under treatment in the study. In addition, site personnel will record via eCRF any change in the condition(s) and any new condition(s) as AEs. Investigators should record their assessment of the potential relatedness of each AE to protocol procedure or investigational product via eCRF.

The investigator will decide whether he or she interprets the observed AEs as reasonably possibly related to migraine, to the investigational product, study device, study procedure, or other concomitant treatment or pathologies. The investigator will answer yes/no when making this assessment.

Planned surgeries and nonsurgical interventions should not be reported as AEs unless the underlying medical condition has worsened during the course of the study.

If a patient's investigational product is discontinued as a result of an AE, study site personnel must report this to Lilly or its designee via eCRF, clarifying if possible, the circumstances leading to discontinuations of treatment.

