### 9.4.5. Safety Monitoring

Investigators are responsible for monitoring individual patient safety throughout the trial. If a study patient/subject experiences elevated ALT  $\geq 3$ -fold ULN, ALP  $\geq 2$ -fold ULN, or elevated TBL  $\geq 2$ -fold ULN, clinical and laboratory monitoring should be initiated by the investigator. Details for hepatic monitoring depend upon the severity and persistence of observed laboratory test abnormalities. To ensure patient/subject safety and comply with regulatory guidance, the investigator is to consult with the Lilly Medical representative regarding collection of specific recommended clinical information and follow-up laboratory tests. See [Appendix 4](#).

Neurological examinations will be conducted at screening, Month 3, and Month 6 of treatment, as well as at the final visit of the post-treatment follow-up period or early termination visit in order to assess for any signs of preexisting or treatment-emergent neurological abnormalities such as stroke or other cerebrovascular events. If a study patient experiences signs of a cerebrovascular event, appropriate follow-up and clinical management should be conducted by the investigator, and the Lilly Medical representative should be consulted regarding collection of further clinical information and follow-up testing.

Lilly will periodically review evolving aggregate safety data within the study by appropriate blinded methods.

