#### 9.4.5.1. Hepatic Safety Monitoring

If a study patient experiences elevated ALT  $\geq 3$ -fold ULN, ALP  $\geq 2$ -fold ULN, or elevated TBL  $\geq 2$ -fold ULN, liver testing ([Appendix 4](#)) should be repeated within 3 to 5 days including ALT, AST, ALP, TBL, direct bilirubin, gamma-glutamyl transferase, and creatine kinase to confirm the abnormality and to determine if it is increasing or decreasing. If the abnormality persists or worsens, clinical and laboratory monitoring should be initiated by the investigator and in consultation with the study medical monitor. Monitoring of ALT, AST, TBL, and ALP should continue until levels normalize or return to approximate baseline levels.

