#### Hepatic Safety Data Collection

Additional safety data should be collected via the CRF if 1 or more of the following conditions occur:

- elevation of serum ALT to  $\geq 5$ -fold ULN on 2 or more consecutive blood tests
- elevated serum TBL to  $\geq 2$ -fold ULN (except for cases of known Gilbert's syndrome)
- elevation of serum ALP to  $\geq 2$ -fold ULN on 2 or more consecutive blood tests
- patient discontinued from treatment due to a hepatic event or abnormality of liver tests
- hepatic event considered to be a SAE

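### An isolated AST rise above 5-fold ULN has no automatic retest, although Protocol 8.1.1 makes its persistence beyond 2 weeks a reason to consider stopping study drug

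*Protocol*

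**What the plan says.** **Stopping list (Protocol 8.1.1).** Seven liver conditions are given for which discontinuation should be considered after consultation with the medical monitor. Four of them name a transaminase, and all four accept either ALT or AST. One has a duration element: "ALT or AST >5-fold ULN for more than 2 weeks".

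**Monitoring trigger (Protocol 9.4.5).** It begins "If a study patient/subject experiences elevated ALT" and sets thresholds of ALT ≥3-fold, ALP ≥2-fold or TBL ≥2-fold ULN. AST is not named.

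**Repeat trigger (Protocol 9.4.5.1).** For the same three analytes and thresholds, liver testing "should be repeated within 3 to 5 days including ALT, AST, ALP, TBL, direct bilirubin, gamma-glutamyl transferase, and creatine kinase". If the abnormality persists or worsens, monitoring follows: "Monitoring of ALT, AST, TBL, and ALP should continue until levels normalize or return to approximate baseline levels". AST is therefore measured once the process has started, but cannot start it.

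**Hepatic data collection (within 9.4.5.1).** The only line that names a transaminase begins "elevation of serum ALT to" and applies at ≥5-fold ULN on two or more consecutive tests.

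**Schedule (Protocol Section 2).** The row "Clinical chemistry" is marked at Visits 7, 10 and 12 after dosing has begun, and not at Visits 8 or 9. Study drug is given at Visits 8 and 9.

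**The concern.** A criterion of more than 2 weeks cannot be judged on one sample. For ALT, the protocol requires a repeat and, if the rise persists, continued monitoring. For AST alone it requires neither, so the stopping list contains an AST criterion without an automatic supply of the results needed to apply it.

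What is at stake is individual dosing. In a patient who enters the open-label phase, a persistent AST rise first seen in the Visit 7 sample could go unassessed against this criterion before two further doses.

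**Working it through.** The plan states no figure on this point, so the check compares texts and counts days.

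**1. Which AST conditions lack the data they need?** The inputs are the four transaminase conditions in 8.1.1.
- Above 8-fold: one sample decides.
- Above 3-fold with TBL above 2-fold: one sample decides, and TBL ≥2-fold is itself a repeat trigger. The alternative limb, INR above 1.5, is set aside because the repeat panel omits INR for both enzymes.
- Above 3-fold with listed symptoms or eosinophilia: one visit decides.
- Above 5-fold for more than 2 weeks: needs at least two results.

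That leaves 4 − 3 = 1 condition, or 1 of the 7 on the list. It matters for AST above 5-fold and up to 8-fold ULN, with ALT <3-fold, ALP <2-fold and TBL <2-fold ULN and no listed symptom or eosinophilia. Outside those limits another condition or trigger applies.

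**2. What happens after such a result?**

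| Step | ALT above 5-fold | AST above 5-fold, isolated |
|---|---|---|
| Monitoring under 9.4.5 | Triggered | Not triggered |
| Repeat at 3 to 5 days under 9.4.5.1 | Triggered | Not triggered |
| Monitoring until normal or near baseline | If it persists or worsens | Not triggered |
| Duration condition in 8.1.1 | Applies | Applies |

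**3. How long until scheduled chemistry?** Visits 7 to 8, 8 to 9 and 9 to 10 are each 30 ± 2 days. Counting from the Visit 7 sample as day 0:
- Visit 8 dose: 28 to 32.
- Visit 9 dose: 2 × 28 = 56 to 2 × 32 = 64.
- Visit 10 chemistry: 3 × 28 = 84 to 3 × 32 = 96.

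**4. Is there time for a useful retest?** More than 2 weeks is first reached on day 15.
- Before the Visit 8 dose: 28 − 15 = 13 to 32 − 15 = 17 days.
- Before the Visit 9 dose: 56 − 15 = 41 to 64 − 15 = 49 days.

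The documents give no laboratory turnaround. Assuming 1 to 7 days, 13 − 7 = 6 to 17 − 1 = 16 days remain before Visit 8. These figures show the time available. Nothing in the current text secures a sample within it.

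**5. Would adding AST to the triggers be enough?** The dated repeat comes at 3 to 5 days. Even if those days are counted from a result that took the assumed maximum of 7 days, 7 + 5 = 12, which is short of 15. The monitoring that follows has no stated interval. Adding AST makes a later result likelier but does not date it. ALT has the same limitation now.

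**6. Does the data-collection line matter for retesting?** No. It governs what is recorded. Of its five conditions, one names a transaminase (ALT only). Two do not depend on which enzyme is raised: discontinuation for a hepatic event or abnormal liver tests, and a hepatic SAE.

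**The case against.** The strongest case is that a narrow automatic trigger beside a broader, discretionary stopping list is a coherent choice. ALT-led wording recurs in exclusion criterion 24 and in the Hy's law definition in SAP 6.14.3, which suggests intent. An investigator who sees AST above 5-fold has 8.1.1 as a reason to retest, and Protocol 9.2 adds: "Investigators must document their review of each laboratory safety report". The note to the Schedule of Activities and Appendix 4 allow hepatic tests for any treatment-emergent hepatic abnormality and say that they may be required in follow-up, in consultation with the sponsor's physician. AST is in that panel. The sponsor also reviews aggregate safety data by blinded methods (9.4.5).

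Much of this stands. A reader might infer that an isolated AST rise cannot be followed up, or that no one could require a retest. The documents do not support that, because a route to a sponsor-requested retest exists for either enzyme. A reader might also infer that AST-led cases escape hepatic data collection. They do not once the patient is discontinued for abnormal liver tests or has a hepatic SAE. Nor are the AST conditions in general unworkable, since three of the four can be reached without a later AST result.

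What the objection does not supply is a date. Documented review, discretionary AE follow-up (9.2) and optional tests set none. A laboratory finding becomes a reportable AE only when it results in a diagnosis (9.4.3). Aggregate review and the SAP's tables of ALT or AST at ≥3, 5 and 10 times ULN cannot guide one patient's next dose. ALT-led wording elsewhere does not explain why 8.1.1 sets a duration criterion for AST without serial AST results.

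**Conclusion.** The point holds as a minor inconsistency in safety monitoring. One of seven liver conditions is affected, within a narrow laboratory pattern. The exposed case is a rise found at Visit 7 in a patient who opts for open-label treatment, because Visit 7 is the only scheduled post-dose chemistry followed by further dosing visits. There the automatic provisions yield no AST result for 84 to 96 days, with two doses in between.

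This rests on reading the triggers as written and on no one choosing or requesting a retest. How often isolated AST rises of this size occur is not given, so the number of patients cannot be estimated, and some such rises will not be hepatic. The criterion is one to be considered and is not mandatory. Efficacy, power and type I error are untouched.

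**What to change.** 1. In 9.4.5 and 9.4.5.1, change the transaminase trigger to *ALT or AST ≥3-fold ULN*.
2. In 9.4.5.1, add that a transaminase still above 5-fold ULN on the repeat is tested again after day 14, counted from the first such sample, and before the next dose. Step 5 of the working shows why the first edit is not enough alone. For a Visit 7 sample the two timing requirements are compatible, with 13 to 17 days between day 15 and the Visit 8 dose.
3. As a separate consistency edit, write *ALT or AST* in the ≥5-fold data-collection line. This aligns the record with 8.1.1 but does not affect whether AST is retested.

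No new assay is needed, since AST is in the routine panel (Appendix 2) and in the repeat panel. The cost is occasional retests for AST-only rises, at a frequency the documents do not give, and an unscheduled blood draw for those who remain above 5-fold. Creatine kinase, already in the repeat panel, helps to identify rises of muscle origin.
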